9.6 Description Statistics and Listings

Data related to the primary and secondary endpoints will be summarised using descriptive statistics where appropriate, and subject-level data will be provided in data listings.

Product usage will be summarised using descriptive statistics (total amount used and number of times product was used). Sexual activity will be summarised using descriptive statistics.

9.7 Adverse Events

AEs from both the Tolerance Phase and Treatment Phase will be summarised together. Safety endpoints will include incidence of treatment-emergent AEs (TE AEs), ADEs (TE ADEs) and concomitant medications.

The MedDRA (the most recent version) will be used to classify all AEs with respect to system organ class and preferred term. AE summaries will include only TE AEs and TE ADEs, which will be summarised (incidence and frequency) for each treatment group. In addition, TE AEs and TE ADEs will be summarised according to relationship to the device and study procedures. AEs for females and their male partners will be summarised separately.

Concomitant medication usage will be listed.

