1.7 Benefits / Risks Assessment

This investigation has been designed to evaluate the effectiveness and safety of two personal vaginal lubricants: [REDACTED] Subjects in this investigation are females who experience intimate discomfort associated with vaginal dryness during sexual intercourse. Such investigational population are expected to experience a level of relief from intimate discomfort during sexual intercourse with the use of their allocated IP.

Additionally, each subject will undergo a physical examination, including a gynaecological examination as part of enrolment into the investigation to confirm that the subject is sexually healthy as defined in this investigation. The examination is a standard gynaecological examination, however due to the indication of vaginal dryness, the examination may be unpleasant or painful depending on the severity of the subject's symptoms. Slight bleeding due to injury to the skin may occur when inserting the speculum. Subjects with underlying conditions identified through the physical examination will be referred as appropriate. [REDACTED]

[REDACTED]

Only those subjects who meet the eligibility criteria set out in this investigation, and as assessed by the Investigator as being suitable to enter into the investigation will be enrolled. Subjects of childbearing potential will be required to be on a highly effective form of contraception before being enrolled into the investigation, additionally subjects will be screened for sexually transmitted infection (STI), however in the event that the subject become pregnant or contracts an STI they will have access to the clinical site where appropriate follow-up measures will be taken.

subjects who experience any untoward medical occurrence during the investigation have access to the Investigator/clinical site where appropriate measures will be taken. Additionally, the Investigator (in consultation with the gynaecologist) will determine if a subject remains eligible to move into the Treatment Phase of the investigation after the completion of the Tolerance Phase, as per the inclusion/exclusion criteria and provided that the subject has not experienced any untoward medical occurrence.

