To assess the effects of two personal lubricants on the impression of change in the sexual intimacy between female subjects and their male partners.	
 Number and percentage of female subjects recording ≥ 2 improvement in sexual intimacy on the Patient Global Impression of Change (PGIC) at 4 weeks. Number and percentage of male partners recording ≥ 2 improvement in sexual intimacy on the PGIC at 4 weeks.

[figure not shown]
Tolerance Phase

Secondary Objectives	Secondary Endpoints
To assess vulvovaginal tolerance of two personal lubricants in women who experience intimate discomfort associated with vaginal dryness.	
 An assessment of the Vaginal Epithelial Tolerability (VET) of the two personal lubricants at baseline, 2 and 24 hours post single application as assessed by gynaecologist examination. Subject Perception of Vulvovaginal Tolerance of the two personal lubricants will be determined through Subject Perceived Questions at 24 hours post single application. A Global Assessment of Vulvovaginal Tolerance for each subject at 24 hours post single application as determined by the gynaecologist. Overall Vulvovaginal Tolerance Rating Statement for each personal lubricant as determined by the gynaecologist.
To assess oral mucosal tolerance of two personal lubricants in women who experience	
 An assessment of the Oral Mucosal Tolerance of the personal lubricants at

intimate discomfort associated with vaginal dryness.	
baseline, 30 minutes, 2 and 24 hours post single application to the upper and lower inner lip as assessed by dermatologist.
 
 • Subject Perception of Oral Mucosal Tolerance of the two personal lubricants will be determined through Subject Perceived Questions at 24 hours post single application. • Global Assessment of Oral Mucosal Tolerance for each subject at 24 hours post single application as determined by the dermatologist. • Overall Oral Mucosal Tolerance Rating Statement for each personal lubricant as determined by the dermatologist.

Tolerance Phase and Treatment Phase

Safety Objective	Safety Endpoint
To assess the safety and establish the safety profile of two personal lubricants in women who experience intimate discomfort associated with vaginal dryness.	Overall proportion of subjects with Adverse Events/Adverse Device Effects (AE/ADEs) i.e. the occurrence of one or more AE/ADE per subject.

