To assess the safety and establish the safety profile of two personal lubricants in males.	Overall proportion of males with Adverse Events/Adverse Device Effects (AE/ADEs) i.e. the occurrence of one or more AE/ADE per male partner.

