6.13 Adverse Events

During scheduled visits, non-leading questions ('Are you experiencing any symptoms or complaints? / Have you felt unwell, suffered any complaints or taken any medication since... / Have you had any symptoms of complaints since the last time you were asked?') will be used to collect any AE/ADE experienced by the subject/male partner. Additionally, spontaneously reported AEs/ADEs will be collected. AE/ADE of male partners can be reported via a contact by the male partner with the clinical site or via the female subject at each visit or via the male partner at his visit.

The observation period for an individual subject/male partner will start after giving informed consent and will finish at the last visit of the Treatment Phase for the given individual subject/male partner. All AEs/ADEs that arise during the observation period will be recorded and an assessment of the AEs/ADEs will be performed as per [Section 8.1](#) by a medically qualified Investigator. If a subject/male partner has an AE/ADE that is still ongoing at the last visit, an attempt will be made by the Investigator to follow this up as per [Section 8.3](#).

If an untoward medical occurrence happens after the subject/male partner has signed the consent form but before administration of the device, it should be reported as an AE, including those associated with investigation procedures.

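### The safety endpoint is any AE/ADE, but Section 9.7 summarises only treatment-emergent events, a term left undefined, so pre-product and screening-examination AEs may appear only in listings

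*Combined protocol and SAP*

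**What the plan says.** **The endpoint.** Section 2.1, Table 2-1, gives the safety endpoint for women as: "Overall proportion of subjects with Adverse Events/Adverse Device Effects (AE/ADEs) i.e. the occurrence of one or more AE/ADE per subject". The row for men has the same form: "i.e. the occurrence of one or more AE/ADE per male partner". The synopsis list of secondary endpoints agrees. None of these rows carries a treatment-emergent qualifier or a time window.

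**Collection.** Under Section 6.13 the observation period "will start after giving informed consent and will finish at the last visit of the Treatment Phase". An untoward occurrence after consent but "before administration of the device, it should be reported as an AE, including those associated with investigation procedures".

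**Analysis.** Section 9.7 restates the endpoint: "Safety endpoints will include incidence of treatment-emergent AEs (TE AEs), ADEs (TE ADEs) and concomitant medications". It then sets the rule: "AE summaries will include only TE AEs and TE ADEs, which will be summarised (incidence and frequency) for each treatment group". The procedure table follows that rule: "TE AEs and TE ADEs will be summarised according to relationship to the device and study procedures". AEs from the Tolerance and Treatment Phases are pooled, with women and men shown separately. The Statistical Evaluation part of the synopsis also limits summaries to treatment-emergent events, but it adds severity, which Section 9.7 does not mention.

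**The named procedure risk.** Section 1.7 warns about the gynaecological examination: "Slight bleeding due to injury to the skin may occur when inserting the speculum".

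**Definition.** The abbreviation list expands the treatment-emergent terms. No section in the visible text says which application starts the clock.

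**The concern.** The endpoint listed in Table 2-1 has no analysis that reports it as worded. The proportion that Section 9.7 produces covers a narrower set of events, and its boundary is undefined.

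Two consequences follow under the usual meaning of the term. First, the table meant to show harm from study procedures cannot count an injury from the screening examination, although that examination carries the procedure risk the plan itself names. Second, a woman's run-in events are counted or not according to whether she was in the tolerance subset, yet both kinds of women go into one percentage per treatment group. A reader of the report would not know which events the safety proportion covers.

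**Working it through.** The plan states no AE rate, so there is no figure of its own to reproduce. The check compares the sections and then counts planned observation time.

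**1. Where the screening examination falls.** Section 7.2 requires a gynaecological examination at screening. Randomisation follows completion of screening (notes to Table 7-1), so for all 66 women it precedes any product. At Treatment Phase Visits 2 and 3 the examination is done only if the investigator judges it necessary (Sections 7.4.2 and 7.4.3). For the direct entrants, 66 - 22 = 44 women, screening is therefore the only scheduled gynaecological examination. The 22 tolerance women also have a baseline vaginal assessment before application (Section 7.3.2) and further assessments at 2 and 24 hours after it.

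**2. Where the run-in falls.** Product for home use is dispensed after the 4-week run-in (Section 7.4.2). Tolerance women have already had one application before their run-in starts (Sections 7.3.2 and 7.4.1).

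**3. Effect of the definition.**
- If treatment-emergent means onset after the first application in either phase, which the pooling of phases suggests, screening-examination AEs are out for all 66 women. Run-in AEs are out for the 44 women and in for the 22.
- If it means onset from the start of the Treatment Phase for direct entrants, their run-in AEs would count, because Section 3.1 places the run-in inside that phase. Screening-examination AEs would still be out.

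**4. Planned time before first product, first reading.** Direct entrants have 28 run-in and 28 use days. Tolerance women have 7 to 10 wash-out days, 1 day to the 24-hour visit, 28 run-in and 28 use days. Drop-out is ignored.
- Women, 7-day wash-out: (44×28 + 22×7) / (44×56 + 22×64) = 1,386 / 3,872 = 35.8%.
- Women, 10-day wash-out: (44×28 + 22×10) / (44×56 + 22×67) = 1,452 / 3,938 = 36.9%.
- Men, assuming first exposure is in the use period, 7 days: (44×28 + 22×36) / 3,872 = 2,024 / 3,872 = 52.3%.
- Men, 10 days: (44×28 + 22×39) / 3,938 = 2,090 / 3,938 = 53.1%.
- Female run-in days after first product: 22×28 = 616 of 66×28 = 1,848, or 33.3%.
- Counted days per woman: 28 for a direct entrant, 1 + 28 + 28 = 57 for a tolerance woman.

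**5. Illustration only.** Assume a constant weekly AE rate h, the same before and after product, and a 7-day wash-out. The proportion of women with any AE is then:
- from consent: [44(1 - e^(-8h)) + 22(1 - e^(-64h/7))] / 66
- treatment-emergent: [44(1 - e^(-4h)) + 22(1 - e^(-57h/7))] / 66

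| Assumed h per week | From consent | Treatment-emergent only |
|---|---|---|
| 0.02 | 15.4% | 10.1% |
| 0.05 | 34.2% | 23.2% |
| 0.10 | 56.7% | 40.5% |

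These rates are assumptions. The table shows the direction and a possible range, not an estimate.

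**6. Denominator.** Section 9.3 makes the Safety Population all randomised subjects. A woman who leaves before any product is in the denominator but cannot have a treatment-emergent event on the first reading.

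**The case against.** Collecting AEs from consent and tabulating only treatment-emergent ones is ordinary practice. The stated objective is the safety profile of the lubricants, which events before exposure do not inform. Section 9.7 and the synopsis statistics agree with each other, so the endpoint rows may simply lack a qualifier. Section 9.1 leaves details to a SAP, which may define the term. Pre-product events are not lost: Section 9 has all data listed, Section 8.2 requires every AE to be recorded, and 66 women is few enough to read the listings directly.

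Most of this stands, and it rules out several stronger readings that a reader might infer:
- *The endpoint itself counts from consent.* It does not say so. The consent start is the collection rule in Section 6.13.
- *Run-in events never enter the summaries.* They would for the 22 tolerance women on the reading that pooling implies.
- *Procedure harm will look close to zero.* AEs from examinations after application, such as those at 2 and 24 hours, can still enter the procedure table.
- *The run-in is the trial's internal control for AEs.* No section plans that comparison, and a third of the women have had product before their run-in.

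What the objection does not answer is that the term has no visible definition, the listed endpoint has no analysis that matches its wording, and the procedure table omits the mandatory examination whose risk Section 1.7 names.

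**Conclusion.** The point holds in limited form and is a cheap improvement. Followed as written, Section 9.7 leaves the Table 2-1 safety endpoint unreported and undercounts AEs from study procedures. The primary analysis and the collection of safety data are not affected.

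Only the planned time can be sized: about 36% to 37% of female and 52% to 53% of male-partner observation precedes exposure. This assumes that treatment-emergent means onset after first application in either phase, that men are first exposed in the use period, and that all complete the schedule. The exclusion of screening-examination AEs is firmer, since it holds under both readings considered. The gap in the AE percentage itself is unknown.

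**What to change.** In Section 9.7, or in the SAP:

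1. Keep the treatment-emergent tables. Define the term by naming the reference application, covering both phases, and stating it separately for women and men.
2. Report the Table 2-1 endpoint as n (%) with any AE/ADE from consent, for women and men separately, split by onset before and onset on or after first product.
3. Base the table of relationship to study procedures on all AEs from consent.
4. Add the severity summary that the synopsis already states.

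The cost is some wording and one or two extra tables. AEs are already recorded from consent, so no new visit or assessment is needed. The team should confirm that the eCRF captures relationship to procedures for non-serious events before product. The overall AE percentage will be somewhat higher, and the split by onset shows why.

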9.8 Handling of Missing Data and Drop-outs

All data will be analysed as collected; missing data due to premature discontinuation or any other reason will be left as missing. For the FSFI, in order to minimise the number of missing values for the FSFI subscale and Total scores, missing item responses will be handled as follows. A subscale score will be calculated as long as at least half of the items on the given subscale have valid, non-missing responses. Specifically, each subscale must have at least two non-missing responses, except for Desire, which has only two items and requires only one non-missing response. The Total FSFI score will be calculated as long as at least five out of the six subscale scores are present. Scores calculated in the presence of missing items will be pro-rated so that the theoretical minimum and maximum values are the same as those scores from complete data.

10 DATA HANDLING AND RECORD KEEPING

10.1 Case Report Forms

For each enrolled subject, an eCRF using fully validated software that conforms to 21 CFR Part 11 requirements, will be maintained. In the event of a screen failure, data will be recorded in the eCRF up until the point of screen failure. The Investigator is responsible for the quality of the data recorded in the eCRF. The data recorded should be a complete and accurate account of the subject's record, collected during the study. Subjects and male partners must not be identified in the eCRF by name or initials.

The Investigator and clinical site staff who have been delegated responsibility for entering data into the eCRF at each visit will be trained in the use of the eCRFs before being given access to the eCRF and before the first subject first visit. The Investigator must certify that the data entered into the eCRF is complete and correct.

The Investigator agrees to complete the eCRFs in a timely fashion after completion of each subject and make them available to the study monitor for full inspection. In addition, any data queries raised should be answered promptly. Following monitoring and data management review of each subject's eCRF, the Investigator will electronically sign the eCRF. Re-signature by the Investigator may be required prior to database lock after resolution of data queries identified at the data review meeting.

Before acceptance, the study monitor will review the eCRFs for completeness and adherence to the protocol. Upon completion of monitoring and once Data Management has entered data into the database, performed all edit checks, and all queries answered, the study database will be declared clean and all access will be removed.

10.2 Specification of Source Documents

Source data must be available at the clinical site to document the existence of the investigational subjects. Source data must include the original documents relating to the investigation, as well as the medical treatment and medical history of the subject. The Investigator and monitor will identify the data that will be recorded directly on the eCRF and for this data the eCRF will be considered the source document (i.e. no prior written or electronic record of the data). The monitor will confirm this at the Initiation Visit.

Source data (e.g. ICF, medical history, concomitant medication, questionnaires) contained in the subject records will be held in the ISF.

Where source data are in the form of a computer print-out (e.g. laboratory data) they will be signed and dated by the Investigator, confirming that the print-out is a true and faithful record of the data. These print-outs will be filed in the ISF.

The Investigator agrees to provide direct access to source data for investigation-related monitoring, audits, IEC / REC / IRB review, and regulatory inspection(s). Direct access to source data requires that the subject gives written, documented consent to this.

No investigation records should be destroyed without prior written agreement by the Sponsor.

10.3 Data Management

The data management group at the CRO will be responsible for eCRF development and data management activities.

Access to the eCRF will be by password and the eCRF will be backed up.

Any changes made by the Investigator and clinical site staff who have been delegated responsibility for entering data into the eCRF will be captured via an audit trail in the system.

Automatic validation programs check for data discrepancies and, by generating appropriate error messages, allow the data to be confirmed or corrected before transfer of the data to the Biometrics group. The monitor is also able to raise queries in the eCRF as required.

Coding will be done manually outside of the eCRF and checked. Coding of AEs/ ADEs and medical history will be done using the most recent version of MedDRA V25.1 (or the most recent version if this has changed during the course of the clinical investigation) by the CRO.

Concomitant medications will be coded by the CRO using the latest version of the WHO dictionary (including ATC coding). All coding will be checked by the Sponsor using the most up-to-date version of MedDRA and WHO dictionary.

10.4 Reporting of CIP Deviations

Site staff should make monitor aware of any deviation from the CIP as soon as possible after occurrence. Waivers for inclusion / exclusion criteria are not allowed.

10.5 Retention of Essential Documentation

The Investigator should retain all essential documents (as defined in ICH E6 or according to other national and international regulations) until at least 10 years after the completion of the investigation (defined as last subject last visit in the investigation). These documents should be retained for a longer period, however, if required by the applicable regulatory requirements or by an agreement with the Sponsor. It is the responsibility of the Sponsor to inform the Investigator when these documents no longer need to be retained.

Subject files and other source data must be kept for the maximum period of time permitted by the Clinical Unit, hospital, institution or private practice. The Investigator must notify the Sponsor of the retention period if this is shorter than described above.

11 QUALITY CONTROL AND QUALITY ASSURANCE

11.1 Monitoring

The Sponsor/CRO will organise regular monitoring visits to be performed at intervals agreed with the Investigator. The anticipated monitoring frequency will be stated in the Monitoring Plan. Monitoring will also involve, as appropriate, correspondence and telephone contacts.

On-site monitoring includes source data verification (SDV) which is the procedure whereby the data contained in the eCRFs are compared with the primary source data and thereby verified as accurate. It will be performed in such a way as to preserve subject confidentiality, taking into account all ethical and legislative requirements. The Investigator or designated clinical site staff, must be available at some time during the monitoring visit to review the data and resolve any queries and to allow direct access to the subject's records for SDV.

SDV will include as a minimum verification for all subjects and male partners, subject/male partner identity (age, sex and subject number), record of entry into the study and signature of the informed consent. In addition, details of SAEs in the subject's notes will be verified. Details included in the subject's notes as a minimum:

- Clinical Investigation number, brief description or title of study
- Date that the subject gave written consent
- All visit dates
- All SAEs
- All concomitant medications

At a site visit the eCRFs should be complete and available in order that the accuracy of their completion may be checked. Each completed eCRF for each subject must be signed electronically by the Investigator, to verify the data and statements submitted. Similarly, all alterations on paper

D8199934 V6.0, Appendix 2 – Clinical Investigation Plan

Change Control: CC220523-009

 HEALTH • HYGIENE • HOME	Clinical Investigation Plan		
	Investigation No:	Protocol Version:	Page 86 of 96

records must be initialled and dated by the Investigator or designated clinical site staff, explained as necessary, with the original mistake left legible.

